### 893        **3.11 Treatment of Amblyopia**

894        Patching, Bangerter foils, and binocular treatment for amblyopia are allowed at investigator  
895        discretion during the study. However, atropine and other cycloplegic drops, and/or bifocal lenses  
896        prescribed for treating amblyopia are not allowed.

### 897        **3.12 Spectacle Tolerance Criteria for Follow-up**

898        The following spectacle tolerance criteria will apply throughout the study (unless previously  
899        released to treatment at investigator discretion):

- 900        a. Spectacles (HOME and OFFICE) must meet the following spectacle tolerance  
901        criteria as compared with the participant's most recent cycloplegic refraction  
902        (NOTE: if hyperopic sphere and/or the bifocal add power has been reduced per  
903        protocol, sphere and add power must be within tolerance of what was prescribed):  
904            • SE refraction must be corrected within  $\pm 0.625$  D  
905            • Sphere power must be corrected within  $\pm 0.50$  D  
906            • Anisometropia must be corrected within  $\pm 0.50$  D SE  
907            • Cylinder power must be corrected within  $\pm 0.50$  D  
908            • Cylinder axis must be within  $\pm 10$  degrees if cylinder power is  $\leq 1.00$  D, and  
909            within  $\pm 5$  degrees if cylinder power is  $> 1.00$  D.  
910            • Bifocal must be a flat-top 35 and meet the following tolerance criteria:  
911              ○ Height must be within  $\pm 2$  mm of mid-pupil  
912              ○ Power must be within  $\pm 0.50$  D of that prescribed  
913              ○ Total sphere power of the bifocal segment must be corrected within  
914               $\pm 0.50$  D of the sum of the prescribed bifocal power and distance  
915              sphere power  
916              ○ Measured bifocal add power (lensometry difference between  
917              distance sphere power and bifocal sphere power) must be within  
918               $\pm 0.50$  D of prescribed bifocal add power

919 **3.12.1 Change in Spectacles Because Lensometry Reveals Spectacles are Out of Tolerance**  
920 When lensometry reveals that the spectacles do not meet spectacle tolerance criteria (section  
921 3.12) based on the most recent spectacle prescription (which includes any reduction in hyperopic  
922 sphere and bifocal add power) and the most recent cycloplegic refraction, the spectacles must be  
923 remade.

924 **3.13 Management of Refractive Error During Follow-up**

925 **3.13.1 Change in Spectacles Following a Change in Cycloplegic Refraction**

926 If a cycloplegic refraction during follow-up reveals a change in refractive error such that the  
927 current spectacles do not correct the refractive error to within spectacle tolerance criteria (section  
928 3.12) then both HOME and OFFICE spectacle corrections must be updated (new lenses  
929 prescribed).

930 The new spectacles must be prescribed based on the most recent cycloplegic refraction and the  
931 full correction for hyperopia, myopia, and astigmatism is to be prescribed. Those randomized to  
932 the BFL group also will be prescribed a +3.00 D add.

- 933 • NOTE: No reduction in hyperopic correction or bifocal add is permitted when initially  
934 prescribing required new spectacles during follow-up; however, a reduction in hyperopic  
935 correction or bifocal add can be made at a subsequent visit, if warranted (see sections  
936 3.13.2 and 3.13.3).

937 **3.13.2 Reduction of Hyperopic Correction Because of Distance Blur**

938 The initial study spectacles will be prescribed with the full-plus hyperopic correction. However,  
939 if one of the following occurs at any time during follow-up, the investigator may reduce the  
940 distance hyperopic correction (sphere) symmetrically by 0.25 D or 0.50 D from the original  
941 randomized prescription. Hyperopic correction may be reduced if the participant:

- 942 (1) has a decrease in VA of 0.2 logMAR or more (based on conversion of Snellen  
943 equivalent to logMAR. (See Table 1 in section 2.2),  
944 (2) complains of distance blur (even if VA has not decreased), or  
945 (3) resists wearing the spectacles and the investigator believes the resistance may be from an  
946 inability to relax accommodation fully

948 **3.13.3 Management of Refractive Error to Control Exodeviations**

949 If at any time during follow-up a participant develops a constant exotropia at NEAR, the  
950 investigator should determine the amount of reduced hyperopic correction in the reading portion  
951 of the lens (bifocal add for the BFL group and spherical component of the entire lens for the SVL  
952 group) necessary to reduce the frequency of the exotropia such that it is no longer constant **AND**  
953 **contact one of the Protocol Chairs** prior to making any changes.

954 If at any time during follow-up the child develops an exodeviation at DISTANCE (constant,  
955 intermittent, or phoria), the investigator should determine the amount of reduced hyperopic  
956 correction necessary to reduce the exodeviation to ortho or a small amount of esodeviation **AND**  
957 **contact one of the Protocol Chairs** prior to making any changes.

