402 requirements outlined for each group above. However, if the participant is having problems with  
403 blurred vision, then the prescription may be adjusted when the child returns for follow-up as  
404 described in section 3.13.2. If the participant develops constant exotropia at near or any type of  
405 exodeviation at distance (constant XT, IXT, or exophoria), the prescription may be adjusted as  
406 described in section 3.13.3, **AFTER calling one of the Protocol Chairs.**

407 Participants in both treatment groups (SVLs and BFLs) will also be prescribed a pair of single-  
408 vision spectacles to be used for near testing and to facilitate in-office masking of examiners.  
409 These spectacles are referred to as the **OFFICE spectacles** and will be sent to the enrolling site  
410 where they will be stored on site and used only for testing purposes at study visits (see *ETS3*  
411 *Manual of Procedures*). The lens power will be +3.00 D more than the full distance correction  
412 (i.e., same refractive correction as measured through the BFL add, but made as single-vision  
413 spectacles). These OFFICE spectacles will be used for masking purposes during follow-up visits;  
414 they will not be sent home with the participant. Throughout the study, any prescription changes  
415 that are made to the HOME spectacles for any reason (see sections 3.12.1, 3.13.2 and 3.13.3)  
416 will also be made to the OFFICE spectacles at the same time.

417

418

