**1. Lensometry:**

- Spectacles (HOME and OFFICE) must meet the following spectacle tolerance criteria as compared with the participant's last prescribed refractive correction (NOTE: if the hyperopic sphere and/or bifocal add power have been reduced per protocol [see sections 3.13.2 and 3.13.3], the sphere and add power must meet the spectacle tolerance criteria as compared with what was last prescribed):
  - SE refraction must be corrected within  $\pm 0.625$  D
  - Sphere power must be corrected within 0.50 D
  - Anisometropia must be corrected within  $\pm 0.50$  D SE
  - Cylinder power must be corrected within  $\pm 0.50$  D
  - Cylinder axis must be within  $\pm 10$  degrees if cylinder power is  $\leq 1.00$  D, and within  $\pm 5$  degrees if cylinder power is  $> 1.00$  D.
  - If bifocals, bifocal must be a flat-top 35 and meet the following criteria:
    - Height must be within  $\pm 2$  mm of mid-pupil
    - Power must be within  $\pm 0.50$  D of that prescribed
    - Total sphere power of the bifocal segment must be corrected within  $\pm 0.50$  D of the sum of the prescribed bifocal power and distance sphere power
    - Measured bifocal add power (i.e., dioptric difference between distance sphere power and bifocal sphere power) must be within  $\pm 0.50$  D of prescribed bifocal add power.
- If at any follow-up visit the participant's spectacles (HOME or OFFICE) do not meet these spectacle tolerance criteria (above) based on the most recent cycloplegic refraction and with allowed adjustments to the most recent prescriptions as outlined in sections 3.13.2 and 3.13.3, then the spectacles must be remade. NOTE that if the spectacles are found to be out of tolerance at any follow-up visit, testing should be performed in trial frames rather than requiring the participant to return for another visit.

- 509 2. Diplopia Assessment: Assess diplopia presence and frequency over the last week by parental  
510 report. If present, classify diplopia frequency as “2 times or less per day” or “more than 2  
511 times per day.”
- 512 3. Monocular Visual Acuity Testing: Distance VA will be measured (right eye first) with the  
513 participant wearing their HOME spectacles and without cycloplegia, using the same test  
514 method used at enrollment.
- 515     • ATS-HOTV; e-ETDRS; OR crowded single-optotype or single-line HOTV, LEA  
516         SYMBOLS, or Snellen letters (Allen pictures and Tumbling E optotypes are NOT  
517         allowed)

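### Section 3.13.2 counts the permitted plus reduction from the original randomized prescription, which is the wrong reference once the sphere has been updated

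*Protocol*

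**What the plan says.** Three parts of the Protocol bear on how far plus may be cut.

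- **Section 3.13.1 (update).** When a refraction shows the lenses to be out of tolerance, they are replaced: "The new spectacles must be prescribed based on the most recent cycloplegic refraction and the" full correction is given. The NOTE bars any cut at that first prescribing. It then says that a reduction in hyperopic "correction or bifocal add can be made at a subsequent visit, if warranted (see sections" 3.13.2 and 3.13.3).
- **Section 3.13.2 (reduction).** The section opens: "The initial study spectacles will be prescribed with the full-plus hyperopic correction". If acuity falls, blur is reported or the child resists the lenses, the investigator may, at any point in follow-up, lower the "distance hyperopic correction (sphere) symmetrically by 0.25 D or 0.50 D from the original" randomized prescription. No other reference is given for a child whose lenses have since been updated.
- **Sections 3.3 and 3.4 (testing and remaking).** The trial-frame instructions in both sections, and the rule in the 3.3 lensometry step on when spectacles must be remade, start from the latest cycloplegic refraction. They describe changes under 3.13.2 and 3.13.3 as adjustments to the latest prescription.

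Section 2.8 adds that prescription changes "that are made to the HOME spectacles for any reason (see sections 3.12.1, 3.13.2 and 3.13.3") are made to the OFFICE pair at the same time.

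**The concern.** Section 3.13.1 expects a child in updated lenses to be able to have a small cut in plus, and names 3.13.2 as the rule for it. Section 3.13.2 then measures the cut from a lens the child may no longer wear. Sections 3.3 and 3.4 assume the opposite reference, so the operative sentence disagrees with the text around it.

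The lenses are part of the outcome measurement. Distance alignment, which decides distance motor failure, is tested through the top of the HOME lenses. Near stereoacuity failure is decided in the OFFICE lenses, which copy every HOME change. A child could therefore be tested further below full plus than intended. Alternatively, a child with blur could be refused a reduction that 3.13.1 allows. Updates are foreseeable: cycloplegic refraction is scheduled at 12, 24 and 30 months, in children enrolled from age 3 to under 9.

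**Working it through.** The Protocol gives no figure to reproduce here. The check is a comparison of the two reference points.

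**Inputs**
- Permitted reduction k = 0.25 or 0.50 D (section 3.13.2).
- Lens at randomization = full correction (section 2.8); call its sphere R.
- Updated lens = full correction of the latest refraction (section 3.13.1) = R + d, where d is the change in cycloplegic sphere since randomization.
- Sphere tolerance = ±0.50 D (section 3.12). Assuming quarter-dioptre steps, an update forced by sphere needs a change of at least 0.75 D from the lens worn.
- Assumed for illustration: R = +4.00 D, cylinder unchanged, and no further refractive change between the update and the reduction.

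**Formulas**
- Literal rule: lens = R − k. Shortfall from current full plus = (R + d) − (R − k) = d + k.
- Rule counted from the latest full-plus prescription: lens = R + d − k. Shortfall = k, whatever d is.

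**Results** (a negative shortfall means more plus than full correction)

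| d | Lens worn after update | Literal lens, k = 0.25 / 0.50 | Literal shortfall | Lens counted from latest full plus | Its shortfall |
|---|---|---|---|---|---|
| 0 | +4.00 | +3.75 / +3.50 | 0.25 / 0.50 | +3.75 / +3.50 | 0.25 / 0.50 |
| +0.75 | +4.75 | +3.75 / +3.50 | 1.00 / 1.25 | +4.50 / +4.25 | 0.25 / 0.50 |
| +1.00 | +5.00 | +3.75 / +3.50 | 1.25 / 1.50 | +4.75 / +4.50 | 0.25 / 0.50 |
| −0.75 | +3.25 | +3.75 / +3.50 | −0.50 / −0.25 | +3.00 / +2.75 | 0.25 / 0.50 |
| −1.00 | +3.00 | +3.75 / +3.50 | −0.75 / −0.50 | +2.75 / +2.50 | 0.25 / 0.50 |

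With no sphere update (d = 0) the two rules coincide. After a rise, the literal cut is too large by exactly d. After a fall of 0.75 D or more, the literal lens is stronger than the one worn, so the permitted reduction cannot be made. The choice of R does not matter, because it cancels from the shortfall.

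**The case against.** The strongest reply is that the intended meaning is clear. Sections 3.3 and 3.4 tie the randomized correction to the latest refraction and speak of adjusting the latest prescription. The 3.3 lensometry step does so for the spectacles themselves, not only for trial frames, and section 3.6 speaks of updated randomized treatment spectacles. The literal reading also defeats itself after a fall in hyperopia, since a reduction that adds plus is no reduction. On this view, *original* means *unreduced*, and its purpose is to stop 0.50 D cuts from accumulating. The rule is also permissive, and few investigators would remove 1.00 D or more of plus from an esotropic child because of one word.

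Most of this stands as evidence of intent, and it keeps the point small. It does not correct the operative sentence. No section defines *original* as unreduced, and the opening of 3.13.2 about the initial spectacles points to the lens given at randomization. The surrounding sections therefore show that 3.13.2 is the sentence out of line.

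Two stronger readings are tempting and are not supported:

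- **Biased failure rates.** A reader might infer that the wrong reference distorts the comparison of arms. The rule is the same for both groups, and the Protocol gives no count of affected children and no link from a given lens error to failure.
- **Tolerance rules that need rewriting.** A reader might note that the 3.3 lensometry step compares with the "last prescribed refractive correction (NOTE: if the hyperopic sphere and/or bifocal add power have been reduced per protocol", that 3.12 says of a reduced lens that "protocol, sphere and add power must be within tolerance of what was prescribed", and that 3.12.1 works "based on the most recent spectacle prescription (which includes any reduction in hyperopic" sphere and add power together with the latest refraction. From this they might conclude that spherical equivalent lacks a consistent reference. Spherical equivalent is sphere plus half the cylinder, so a reference that allows for a reduced sphere naturally carries over to it. Judging a reduced sphere against refraction less reduction would change the 3.12 reference. It could change who is out of tolerance, and so whose failure needs a Failure Confirmation Visit. The wording of 3.13.2 does not justify that.

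Nor should the failure-visit tolerance check be counted on to catch a wrongly referenced lens. For a lens reduced per protocol, 3.12 compares the sphere with what was prescribed.

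**Conclusion.** The point holds as a minor wording error in an operative rule. Once the sphere has been updated, 3.13.2 names a reference that conflicts with the 3.13.1 NOTE and with sections 3.3 and 3.4. For a 0.75 D change, the smallest that forces a sphere update in quarter-dioptre steps, the literal lens is 1.00 to 1.25 D below current full plus after a rise. After a fall it is 0.25 to 0.50 D above.

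Only children with a sphere update followed by a reduction under 3.13.2 are reached. Their number cannot be found from the Protocol, and neither can any effect on failure rates. Investigators who already read *original* as *unreduced* will prescribe as intended. The dioptre figures are worked examples under the stated assumptions, not estimates of what will happen. Sample size and the analysis methods are untouched.

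**What to change.** In section 3.13.2, replace *from the original randomized prescription* with *from the full-plus prescription based on the most recent cycloplegic refraction (maximum total reduction under this section 0.50 D)*. The cap keeps repeated cuts from accumulating, which may be what the present wording was meant to do. Limiting it to this section leaves reductions for exodeviation under 3.13.3 as they are.

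Leave sections 3.12, 3.12.1 and the 3.3 lensometry step unchanged. The cost is one phrase in a protocol amendment and a short memo to sites, with no change to data collection, sample size or analysis.

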## Chapter 4: Testing Procedures and Questionnaires

## 4.1 Clinical Assessments

The following test procedures as described in the *ETS3 Procedures Manual* will be completed for both treatment groups at each visit as specified by the protocol.

1. Monocular Visual Acuity Testing: Monocular distance VA will be tested in both eyes with the participant wearing their study-specified spectacle correction. The right eye is tested, with the left eye occluded with an adhesive patch. The left eye is tested after the right eye. The testing method is at investigator discretion provided the following are used: ATS-HOTV; e-ETDRS protocol; OR crowded single-optotype or single-line HOTV, LEA SYMBOLS or Snellen letters. (Allen pictures and tumbling E optotypes are NOT allowed). Testing does not need to be performed by a study-certified tester and it is not required to be measured on a PEDIG-certified VA testing system, but the chart used needs to be appropriately calibrated. The same testing method must be used throughout the study. Testing time for both eyes typically is in the range of 5 to 7 minutes.
  2. Lensometry: The distance correction and the bifocal add (where applicable) will be measured. Measurement time takes between 1 and 3 minutes and does not involve the participant.
  3. Randot Preschool Stereoacuity Test: The Randot Preschool Stereoacuity Test measures 6 levels (40 to 800 arcsec) of stereoacuity at near (40 cm). Corresponding levels range from 48 to 960 arcsec when tested at 33 cm. The test consists of 3 booklets, each designed to test 2 levels of stereoacuity, and each level consisting of 4 panels, 3 of which contain a random dot stereogram. The participant wears polarized lenses over their spectacle correction. The examiner asks the participant if they can identify a specific black and white shape in the booklet and then asks the participant to point to the panel containing the corresponding stereogram image, as outlined in the *ETS3 Procedures Manual*. The test must be administered by a certified examiner. Testing time is approximately 2-4 minutes.
  4. Distance Randot Stereotest: The Distance Randot Stereotest measures 4 levels (60, 100, 200, and 400 arcsec) of stereoacuity at 3 meters. The test consists of a booklet designed to display 2 pages at a time, each page containing a panel with a single random dot stereogram. The participant wears polarized lenses over their spectacle correction and identifies the stereogram images they see, as outlined in the *ETS3 Procedures Manual*. The test must be administered by a certified examiner. Testing time is approximately 2-4 minutes.
  5. Random Dot Stereo Butterfly Test: The Random Dot Stereo Butterfly Test measures 2000 arcsec of stereoacuity at 40 cm (2400 arcsec at 33 cm). The test consists of a booklet with a single stereogram of a butterfly. The participant wears polarized lenses over their spectacle correction and is asked to pinch the tip of the butterfly's wings, which will appear to float off the page if the participant has stereoacuity. The test must be administered by a certified examiner. Testing time is approximately 1-2 minutes.
  6. Preschool Worth 4-Shape Test: The Preschool Worth-4-Shape test is used to assess a participant's second-degree sensory fusion. The test utilizes a flashlight with 4 back-lit

999 shapes: red heart, green circle, green moon, and white star. The participant views the shapes  
1000 at approximately 33 cm while wearing red/green filter glasses and identifies the shapes that  
1001 are seen as outlined in the *ETS3 Procedures Manual*. The test can determine whether the  
1002 participant has second-degree fusion, suppression, or diplopia. The test must be administered  
1003 by a pediatric ophthalmologist, pediatric optometrist, or certified orthoptist. Testing time is  
1004 approximately 3-5 minutes.

1005 7. Ocular Alignment Testing:

1006 Ocular alignment will be assessed by the cover/uncover test, simultaneous prism and cover  
1007 test (SPCT), and the prism and alternate cover test (PACT) in primary gaze at distance (3  
1008 meters) and at near (33 cm) as outlined in the *ETS3 Procedures Manual*. Testing must be  
1009 done by a pediatric ophthalmologist, pediatric optometrist, or certified orthoptist. Testing  
1010 time is approximately 3-5 minutes.

1011 8. Cycloplegic Refraction: The cycloplegic refraction must be/have been performed 30 to 45  
1012 minutes following at least one application of cyclopentolate 1%. The cycloplegic refraction  
1013 may be done with spectacles off or as an over-refraction in front of the spectacles. Subjective  
1014 refinement is allowed. Testing time is approximately 1-5 minutes (following 30-45 minutes  
1015 of waiting for the cycloplegic drops to take effect).

1016 The following information will be collected by interviewing the parent(s):

1017 1) Assessment of Diplopia: An estimate of the frequency of diplopia (if any) will be determined  
1018 by asking the parent whether “your child has complained of double vision over the last  
1019 week.” If yes, the parent is asked how frequently the child has complained of double vision:  
1020 “2 times or less per day,” “or “more than 2 times per day.” Any study personnel may ask the  
1021 parent to rate diplopia. Testing time is approximately 1 minute.

## 1026 **Chapter 5: Unanticipated Problem and Adverse Event Reporting**

### 1027 **5.1 Unanticipated Problems**

1028 Site investigators will promptly report to the Coordinating Center on an eCRF all unanticipated  
1029 problems meeting the criteria below. Sites must report Unanticipated Problems to the IRB within  
1030 seven (7) calendar days of recognition. For this protocol, an unanticipated problem is an incident,  
1031 experience, or outcome that meets all three (3) of the following criteria:

- 1033 1. Is unexpected (in terms of nature, severity, or frequency) given (a) the research  
1034 procedures that are described in the protocol-related documents, such as the IRB-  
1035 approved research protocol and informed consent document and (b) the characteristics of  
1036 the subject population being studied
- 1037 2. Is related or possibly related to participation in the research (possibly related means  
1038 there is a reasonable possibility that the incident, experience, or outcome may have been  
1039 caused by the procedures involved in the research)
- 1040 3. Suggests that the research places participants or others at a greater risk of harm than was  
1041 previously known or recognized (including physical, psychological, economic, or social  
1042 harm)

1043 The Coordinating Center also will report to the IRB all unanticipated problems not directly  
1044 involving a specific site such as unanticipated problems that occur at the Coordinating Center.  
1045 These instances must be reported to the JCHR IRB within seven (7) calendar days of recognition.  
1046 The Director of the Human Research Protection Program will report to the appropriate regulatory  
1047 authorities if the IRB determines that the event indeed meets the criteria of an Unanticipated  
1048 Problem that requires further reporting.

